Units of 5 sessions will normally be delivered over one week’s time. As is the case with other somatic treatments such as electroconvulsive therapy, some consideration of scheduling flexibility must be made to accommodate holidays and other events. These units of 5 sessions can be delivered over a minimum of 5 calendar days and should be delivered within 12 calendar days. Thus, the entire acute treatment phase would normally take between 4 weeks to 11 weeks. At the end of each treatment block, study staff will enter progress notes for each participant in CPRS. These progress notes will be very brief in nature and contain no results or scores of assessments and will serve simply as records of treatment and assessment. The participant’s primary mental health provider will be listed as an additional signer on these

CSP #556 “The Effectiveness of rTMS in Depressed VA Patients”

Version 4.6, February 2016

Main Section of Protocol

notes. This is to ensure that providers are aware of the veterans progress throughout the study and to maintain an open line of communication with study staff.

Follow-up Phase. After the acute treatment phase ends, all patients will enter a 24 week follow-up period. Taper treatments are considered part of the Follow-up Phase. Follow-up visits will occur approximately monthly during the follow-up phase. These visits should be face-to-face but, in unusual circumstances, telephonic visits may be allowed. Appropriate assessments to measure treatment effects after the acute and follow-up phases will be collected as described in Table 2, Assessments and Frequencies of Administration, in Protocol section VI.G. At the end of each follow-up visit, study staff will enter progress notes for each participant in CPRS. These progress notes will be very brief in nature and contain no results or scores of assessments and serve simply as records of assessment. As on the notes in the acute phase, the participant's primary mental health provider will be listed as an additional signer on these notes.

F. Treatment Regimen

1. Rationale for Selection of rTMS Stimulation Parameters

The Planning Committee's decision regarding the choice of rTMS stimulation parameters in this trial was made in a systematic way with data from three sources.

- a. First, the Planning Committee members performed a thorough literature review of the rTMS antidepressant trials performed over the last 15 years (n=70 trials as of 12/06).

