			Screening/ Baseline	5	10	15	20	[25]	[30/ last]	1	2	3	4	8	12	16	20	24
86	Consent	S*																
01	Screening Form	S																
02	Randomization Form	B*																
03	Baseline	S																
04	Medical History	S																
05	Physical Exam	S							x									
06	Labs	S																
07	Structured Clinical Interview for DSM-IV-TR (SCID-I)	S																
08	Current/Past ATHF	S																
09	Lifetime Drinking History	B																
10	Clinician Administered PTSD Scale (CAPS)	B							x									x
11	Trauma History Questionnaire (THQ)	B																
12	Life Stressor Checklist-revised (LSC-R)	B																
13	Six-Item Blessed Orientation-Memory-Concentration (BOMC)	S																
14	Pregnancy Test	S ²	Every 4 weeks															
15	Medication Use	S	x	x	x	x	x	x	x	x	x	x	x	x	x	x	x	
16	Study Visit Form		x	x	x	x	x	x	x	x	x	x	x	x	x	x	x	
17	Audiometry: REMOVED																	
18	rTMS Treatment Log		x	x	x	x	x	x	x									
19	rTMS Taper Log									x	x	x						
20	Hamilton Rating Scale for Depression (HRSD) and MADRS	S ²	x	x	x	x	x	x	x				x	x	x	x	x	x
21	Beck Depression Inventory (BDI)	B	x	x	x	x	x	x	x				x	x	x	x	x	x
22	Quick Inventory of Depressive Symptomatology (QIDS-C16)	B	x	x	x	x	x	x	x				x	x	x	x	x	x
23	Columbia-Suicide Severity Rating Scale (C-SSRS)	S																
24	Columbia-Suicide Severity Rating Scale (C-SSRS) F/U		x	x	x	x	x	x	x	x	x	x	x	x	x	x	x	x
25	Beck Scale for Suicidal Ideation (BSS)	S	x	x	x	x	x	x	x	x	x	x	x	x	x	x	x	x
26	Beck Hopelessness Scale	S	x	x	x	x	x	x	x	x	x	x	x	x	x	x	x	x
27	Quality of Life (VR 36)	B							x									x

Assessment		Screening/ Baseline	Acute Treatment Phase						Follow-up Phase								
			4 - 11 weeks						24 weeks (6 months)								
			2-4 weeks		End of Session Number ¹				PRN Taper weeks		Weeks						
			5	10	15	20	[25]	[30/ last]	1	2	3	4	8	12	16	20	24
28	Neuropsychological Battery	B						x									x
29	DAST	S						x									x
30	PTSD Checklist (PCL)	B						x									x
31	MAST	S						x									x
32	STAXI-2	S	x	x	x	x	x	x	x	x	x	x	x	x	x	x	x
TLFB	Alcohol/Drug Timeline Followback (TLFB)		x	x	x	x	x	x	x	x	x	x	x	x	x	x	x
33	Urine Tox Screen/Alcohol Test	S		x		x		X		x		x	x	x		x	
34	Termination Form ³																x
35	Control Questionnaire	Before and after the 1 st treatment															x
36	Protocol Deviation	As required															
37	Adverse Events (AE) and ADE and Serious Adverse Events (SAEs) and UADE	As required															

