The Site Monitoring, Auditing and Resource Team (SMART) will conduct monitoring visits to each participating site to monitor investigative records and practices to ensure sites are in compliance with both the study protocol and GCP. These site visits will occur annually or more frequently if directed by the study's Monitoring Plan. Independent quality assurance audits will also be conducted at selected sites, if needed.

7. Special Procedures for Monitoring of Substance Abuse

Under the exclusion criteria, we have listed substance abuse within the previous 90 days because evaluating withdrawal symptoms or cravings in the context of a depression study complicates the evaluation. Furthermore, alcohol withdrawal, cocaine and stimulant abuse, and barbiturate withdrawal are all associated with an increased risk of seizures. More critically, actively abusing drugs or alcohol is associated with a higher risk of completed suicide. Thus, beginning to abuse alcohol or drugs could well be a prelude to a completed suicide and must be immediately addressed.

Prior to study randomization, all potential participants will submit to both an alcohol test and a urine drug toxicology screen. Those that have positive results on either of these tests will be excluded from participation. For those that are eligible for participation, they must also complete alcohol tests and urine drug toxicology screens at randomly at the following time points:

- 1) Acute Treatment Phase: 2nd, 4th, and 6th (if still in acute treatment) weeks
- 2) Taper Phase: 2nd week
- 3) Follow-Up Phase: 1st, 3rd, and 5th months

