Throughout the study, site staff will also monitor participants' use of substances including alcohol, OTC medication, opiates, and street drugs for possible abuse through the use of self-report measures. Prior to each treatment session, study staff will ask participants if they have used any substances in the past 24 hours and if so, how much was used. Study staff will further monitor participants' alcohol and other substance use with weekly administrations of the Alcohol / Drug of Choice Timeline Followback Method (TLFB) (Sobell and Sobell, 1992) during the acute and taper phases of treatment, and monthly administrations of the TLFB during the follow-up phase. The TLFB is a self-report measure of recent drinking behavior or substance abuse. Using a calendar, the patients will retrospectively estimate their daily consumption of alcohol and other substances over the past 7 days prior to the interview. This will enable the study staff to quantify the amount of substances patients are using, therefore tracking changes in

these amounts and addressing problematic substance use at the earliest possible instance. This tool is used for monitoring purposes during the study, not for enrollment.

Participants will also complete the MAST and DAST during screening, at the end of acute treatment, and at the end of the follow-up phase.

Use of substances is not prohibited during study participation; however, participants are discouraged from consuming more than one alcoholic drink per day during their participation. If it is determined that a participant is abusing substances, study staff will alert the SI. At that time, the SI will evaluate the situation and determine if it is appropriate for the participant to continue. The Site PI will use the “VA/DoD Clinical Practice Guideline for Management of Substance Use Disorders” (The Management of Substance Use Disorders Working Group, 2009) as a reference in the evaluation of the situation.

Additionally, during the informed consent process, participants must agree to allow study staff to contact their primary mental health provider should the participant begin to abuse substances during the course of their participation in the treatment trial. Potential participants that do not agree to this portion of the informed consent will not be allowed to enroll.

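### The Timeline Followback keeps a 7-day recall window when interviews become monthly, so in follow-up it covers 25% of days for non-remitters and 37.5% for remitters

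*Protocol*

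**What the plan says.** Section X.B.7 (Special Procedures for Monitoring of Substance Abuse) schedules the TLFB weekly "during the acute and taper phases of treatment" and then sets "monthly administrations of the TLFB during the follow-up phase". The recall period is stated once, with no variation by phase: patients estimate their daily "consumption of alcohol and other substances over the past 7 days prior to the interview". The section says that the record lets staff quantify use, track changes and act early, in its words "addressing problematic substance use at the earliest possible instance". It adds that the tool is for monitoring and not for enrollment. The same section treats a return to abuse as a possible forerunner of suicide that needs an immediate response.

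Table 2 (section VI.G) places the follow-up TLFB at weeks 4, 8, 12, 16, 20 and 24, with further administrations in taper weeks 1 to 3. Section VI.E states that "all patients will enter a 24 week follow-up period" and that "Taper treatments are considered part of the Follow-up Phase". Only remitters receive the taper.

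The other scheduled substance checks are:
- **Alcohol and urine tests:** taper week 2, and then "Follow-Up Phase: 1st, 3rd, and 5th months".
- **MAST and DAST:** once in follow-up, at its end.
- **Questions on the past 24 hours:** only before a treatment session.

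**The concern.** A 7-day look-back fits a weekly interview, because consecutive windows join up. It does not fit a four-week interval, where 21 of every 28 days fall between windows. The protocol fixes both the window and the interval, so this is not a detail left to a later document.

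At stake is the completeness of a safety record. Short bouts of use that end more than a week before a visit leave no trace on the TLFB. The protocol itself regards such patterns as relevant: section VI.G.4 separates binge from regular drinking and says that the pattern may matter for outcome. Section X.B.8 handles suicidal behaviour differently over the same monthly visits, because its C-SSRS criterion covers the whole interval from the previous assessment. The TLFB is justified by the same risk but has no such look-back.

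The other checks do not supply a daily record. Pre-session questions end with the taper and never occur in follow-up for non-remitters. Toxicology falls in three of the six months.

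**Working it through.** The protocol states no coverage figure, so there is none to reproduce. The check is a count of days.

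**Inputs**
- Recall window: 7 days (X.B.7).
- Follow-up length: 24 weeks × 7 = 168 days (VI.E).
- Monthly TLFB visits: weeks 4, 8, 12, 16, 20, 24, six in all (Table 2).
- Taper TLFB visits: weeks 1, 2, 3, remitters only, inside the 168 days (Table 2, VI.E).
- Planned remission: 6% sham and 16% rTMS (VIII.A), or 11% overall with equal arms. Used only for weighting.

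**Coverage = distinct days inside a window ÷ 168**
- Non-remitters: 6 × 7 = 42; 42/168 = 25%. Not covered: 126 days (75%).
- Remitters: (3 + 6) × 7 = 63; 63/168 = 37.5%. Not covered: 105 days (62.5%). From day 22 onward, after the taper, 42 of 147 days are covered, so 71.4% are not.
- Overall at the planned rates: 0.89 × 25% + 0.11 × 37.5% = 26.4% covered, 73.6% not.
- By arm: sham 0.94 × 25% + 0.06 × 37.5% = 25.75%; rTMS 0.84 × 25% + 0.16 × 37.5% = 27.0%. The arms differ by little more than one percentage point.

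**Chance that an episode is missed.** Take a 28-day cycle with a 7-day window at its end, and an episode of *d* consecutive days whose start is equally likely on any day. It is missed if it lies wholly within the 21 uncovered days: P(missed) = max(0, 21 − *d* + 1)/28.

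| Episode length (days) | Calculation | Missed |
|---|---|---|
| 1 | 21/28 | 75% |
| 3 | 19/28 | 68% |
| 7 | 15/28 | 54% |
| 14 | 8/28 | 29% |
| 22 or more | 0/28 | 0% |

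**Delay for ongoing use.** Use that starts and continues is met at the next monthly interview, 0 to 27 days later, with mean (0 + 1 + … + 27)/28 = 13.5 days. The recall window does not enter this calculation; only the interview interval does.

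**With a window back to the last TLFB**
- Non-remitters: 6 × 28 = 168 of 168 days.
- Remitters: 21 taper days, 7 days at week 4, then 5 × 28 = 140; 21 + 7 + 140 = 168 of 168 days.

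**The case against.** Several objections have force.

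- **No outcome rests on the TLFB.** Secondary hypothesis 3 expects substance abuse to improve, and a reader might infer that TLFB relapse counts would test it and be biased low. The protocol does not support that. The secondary outcomes in III.B do not include substance use. Section VI.G.5 gives the assessment of alcohol abuse at baseline, end of treatment and end of follow-up to the MAST, and the DAST follows the same schedule. No relapse count or comparison of TLFB data by arm is defined. A fixed 7-day sample would also not in itself bias average use per sampled day. This objection stands.

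- **The monitoring purpose is not defeated.** A reader might conclude that the stated aim of early action fails. In the acute and taper phases the weekly TLFB serves it. In follow-up, a 7-day window already catches use that is ongoing at the visit, and a longer window would not catch it sooner. This also stands. What remains is that finished episodes are not asked about.

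- **Uncovered by the TLFB is not unobserved.** Toxicology, the final MAST and DAST, four-weekly medication review, continuing care by the VA psychiatrist, and consent for staff to contact the mental health provider all give some sight of use. That is true, but none of them yields a daily record or a routine question about the missing three weeks.

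- **A short window favours accuracy.** Recall over 7 days is better than over 28, and a monitoring tool may reasonably prefer it. This is a real trade-off, and it is why the last 7 days should be kept identifiable.

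- **The form may differ.** The copy of Appendix E at hand stops at the Trauma History Questionnaire, so the TLFB form could not be checked. If it already asks back to the previous visit, only the text of X.B.7 needs correcting.

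**Conclusion.** The gap is real and minor. As section X.B.7 is written, the TLFB leaves 75% of follow-up days uncovered for non-remitters, who are the large majority at the planned remission rates, and 62.5% for remitters. Short, finished episodes are the ones lost; anything lasting 22 days or more is met at the next visit. The result is weaker substance-use monitoring in follow-up. The primary remission endpoint, every defined outcome analysis and the timing of detection of ongoing use are unaffected.

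The day counts assume visits held on schedule, the taper TLFB given in all three weeks to remitters, and the 7-day window applied as written. The miss probabilities further assume a start day spread evenly over the 28-day cycle and accurate reporting within the window. They describe the steady monthly cycle, not a remitter's first four weeks, which are fully covered.

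**What to change.** In section X.B.7 and in the TLFB form instruction, set the window for the monthly follow-up visits to the period since the last TLFB (about 28 days), on the same calendar. Keep 7 days for the weekly acute and taper visits. At each monthly visit, record the latest 7 days separately, so that they stay comparable with the weekly phases.

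This raises follow-up coverage to 168 of 168 days with no added visit or instrument. It costs a wording change, a few more minutes per follow-up visit and less accurate recall for the earlier weeks. It changes only what is recorded and leaves the rules for acting on substance use as they are.

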This is an “intent-to-treat” protocol and any data of patients who are randomized to treatment will be retained for data analyses. As patients will remain under the care of their primary VA psychiatrist before, during and after participation in this study, the patient’s primary VA psychiatrist will remain central to the recruitment, participation and follow-up processes. Throughout a patient’s participation in the study, the site investigator will communicate with the patient’s primary VA psychiatrist to discuss the patient’s condition, reactions and any clinically significant adverse events. If a patient drops out or leaves the study for any reason or is suspended from the study for breaking study rules, every attempt will be made to contact the patient and complete a Termination Form.

J. Missed Visits and Study Termination

If a patient decides to withdraw their consent, a Termination Form will be completed. The Termination Form will include questions regarding the reason for termination and the patient's impression of the efficacy of the treatment to that point. If a patient is lost to follow-up or fails to come to clinic, the patient's primary VA psychiatrist will be informed.

The patient may be terminated from the study at any time if the SI deems that the patient has not been following the protocol. This will generally be done only when the protocol violation significantly increases the risk associated with continuing to participate in the study. A Termination Form will be completed. Patients who are terminated prior to the end of the acute treatment phase will be considered treatment failures.

Any female participant who becomes pregnant during the acute treatment phase of the study will discontinue the study treatments for safety reasons as the effects of rTMS on unborn fetuses is not known at this time and she will immediately enter the follow-up phase. Any female participant who gets pregnant during the follow-up phase of the study will continue to be followed-up in accordance with the protocol and complete all assessments. Women who become pregnant at any time during the study will be asked to sign a release of information in order for the study staff to access the medical records for the outcome of the pregnancy. Women who become pregnant during participation will be referred to an OB/GYN clinic.

K. Follow-up Procedures for Non-remitters and Non-responders

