If at any point someone presents for treatment and is visibly intoxicated, study staff will follow their local VA policy regarding the assessment of intoxication and behavior risk. From that point forward, the participant will be excluded from participation in the study and coded as a treatment failure.

To summarize, stopping criteria for treatment will include:

1. Alcohol use greater than one glass of wine/day or equivalent. Use of alcohol when patient has been warned of serious medication/alcohol interactions, will also fit this criteria. If patients are found to be noncompliant with this, the Site Investigator will decide whether to administer treatment and evaluate the patient's appropriateness for continued participation.
2. Abuse of illegal drugs. If patients are found to be noncompliant with this, the Site Investigator will decide whether to administer treatment and evaluate the

patient's appropriateness for continued participation. An exception to this will be patients who used marijuana up until the past 30 days. Ongoing THC abuse will change the status to "discontinued from the study".

3. Abuse or misuse of prescribed psychiatric medications will also result in either withdrawal from the study or inclusion as a noncompliant patient.

8. Special Procedures for Safety of Potentially Suicidal or Dangerous Patients

Appropriate and frequent assessment of suicidality is important when working with severely depressed individuals. Our approach to this is comprehensive in nature and includes multiple clinical interviews (CSSRS and HRSD) as well as self-report measures (BSS and BHS) that are given at baseline, weekly during acute treatment and the taper phases, and monthly during the follow-up phase. The following criteria will be used for the assessment of suicidality:

Baseline

- a) CSSRS: the endorsement of items 4 or 5, indicating Active Suicidal Ideation with Some Intent to Act, without Specific Plan or Active Suicidal Ideation with Specific Plan and Intent, OR the endorsement of an Actual Attempt, an Interrupted Attempt, an Aborted Attempt, or Preparatory Acts or Behaviors in the 6 months prior to assessment will trigger a clinical evaluation by the Site Investigator, the patient's primary mental health provider, or a mental health emergency clinician.

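### Three substance-abuse rules in Protocol X.B.7 end, or may end, study participation rather than study treatment, against the 24-week follow-up planned for all patients

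*Protocol*

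**What the plan says.** Three rules in Protocol X.B.7 (Special Procedures for Monitoring of Substance Abuse) bear on this.

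- **Visible intoxication.** The rule stands just before the list of stopping criteria and applies whenever someone presents for treatment: "From that point forward, the participant will be excluded from participation in the study and coded as a treatment failure".
- **Ongoing THC abuse** (criterion 2). "Ongoing THC abuse will change the status to" that of a patient discontinued from the study.
- **Misuse of psychiatric medication** (criterion 3). "Abuse or misuse of prescribed psychiatric medications will also result in either withdrawal from the study or inclusion as a noncompliant patient".

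The list is introduced by "To summarize, stopping criteria for treatment will include". For substance abuse in general, X.B.7 says that "the SI will evaluate the situation and determine if it is appropriate for the participant to continue".

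Other sections separate treatment from follow-up. VI.E (Acute Treatment Phase) counts a patient who drops out during treatment as a failure and places that patient in the 24-week follow-up. VI.E (Follow-up Phase) puts every patient into follow-up once acute treatment ends. X.B.9 withdraws a patient with a seizure from study treatments but keeps the protocol assessments. VI.J moves a patient who becomes pregnant during acute treatment straight into follow-up.

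For patients suspended for breaking study rules, VI.I provides an attempt at contact and a Termination Form. VI.H.2 adds 30 days of monitoring of unresolved SAEs. Neither mentions further assessments.

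**The concern.** The list announces criteria for stopping treatment, but two rules take the patient out of the study and a third can. A site that follows them as written would hold no further visits, while VI.E tells the same site to follow everyone for 24 weeks. The protocol words this distinction clearly for seizure and pregnancy, so its absence here leaves sites without a consistent instruction.

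What would be lost is research follow-up: HRSD24 and C-SSRS at the follow-up visits, remission status at 24 weeks, and the substance-abuse scales, for which X.B.7 itself plans: "Participants will also complete the MAST and DAST during screening, at the end of acute treatment, and at the end of the follow-up phase".

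There is a second, narrower problem. Remitters receive taper sessions, which VI.E counts as part of follow-up. A remitter who arrives intoxicated at a taper session is presenting for treatment, so the literal rule codes a failure after the primary endpoint has been determined.

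**Working it through.** **Rules side by side**

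| Event | Section | Treatment | Study assessments |
|---|---|---|---|
| Seizure | X.B.9 | stops | continue |
| Pregnancy in acute phase | VI.J | stops | continue (enters follow-up) |
| Drop-out during treatment | VI.E | stops | continue (enters follow-up) |
| Visible intoxication | X.B.7 | stops | end: excluded from the study |
| Ongoing THC abuse | X.B.7 | stops | end: discontinued from the study |
| Medication misuse | X.B.7 | may stop | may end: one of two options |

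**When each rule can act.** Intoxication is tied to presenting for treatment, so it can arise only at an acute session or, for remitters, in the three taper weeks. Both come before the first follow-up visit at week 4. THC abuse can also be detected later, because toxicology screens are planned for "Follow-Up Phase: 1st, 3rd, and 5th months".

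**Visits at risk.** The protocol gives no frequency for these events. Inputs are 360 patients (VIII.A) and six follow-up visits at weeks 4, 8, 12, 16, 20 and 24 (Table 2). The assumption is that a share f of 1%, 2% or 5% leaves in the acute phase and would otherwise have attended every visit.

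- Planned: 360 × 6 = 2,160 visits.
- Lost: 360 × f × 6.
- f = 1%: 360 × 0.01 × 6 = 21.6.
- f = 2%: 360 × 0.02 × 6 = 43.2.
- f = 5%: 360 × 0.05 × 6 = 108.

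As a percentage of 2,160 this simply returns the assumed f. Under the THC and medication rules an exit could come later and cost less: at most five, three or one visit per patient after a screen at week 4, 12 or 20.

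**MAST and DAST.** Two post-baseline administrations per patient give 360 × 2 = 720 of each scale. If an acute-phase exit loses both, 360 × f × 2 = 7.2, 14.4 or 36 of each are lost.

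**24-week remission.** The planning rates in VIII.A give 180 × 0.16 + 180 × 0.06 = 28.8 + 10.8 = 39.6 remitters. If the same 1% to 5% of remitters left during follow-up, 39.6 × f = 0.4, 0.8 or 2.0 would lack the 24-week result.

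**Primary endpoint.** VI.J and VIII.B.2 count exits before the end of the acute phase as failures, so wording that keeps those patients in follow-up does not change their coding. The exception is a taper-session recoding. III.A sets the endpoint at the end of acute treatment, and VIII.B.2 imposes failure only on drop-outs before that point. Each remitter recoded during taper would move that arm's remission rate by 1/180 = 0.56 percentage points.

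**The case against.** The strongest defence is that the text can be reconciled and that any study exit is deliberate. The THC and medication rules sit under a heading about treatment, neither states that assessments stop, and VI.E already sends drop-outs to follow-up. VI.I, VI.J and Table 2 footnote 3 all foresee suspension or termination from the study. X.B.7 gives reasons for acting on substance abuse: seizure risk, suicide risk and difficulty in evaluating depression. Seizure and pregnancy are medical events, not rule-breaking, so they may be handled differently.

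Part of this stands. For the THC and medication rules the loss of follow-up is an inference from the wording, and for medication it is only one option. The sponsor may terminate patients for cause. But the intoxication rule lies outside the list and excludes the patient from the study in plain terms, which cannot be squared with VI.E. The safety reasons support stopping stimulation; they do not require ending assessments.

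Several stronger readings are tempting, but the protocol does not support them.

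- **A breach of intent-to-treat.** VI.I says only that "any data of patients who are randomized to treatment will be retained for data analyses", and VIII.A and VIII.B.2 define the principle by randomised group with drop-outs as failures. Neither promises further data collection.
- **A bias of known direction in the substance-abuse comparison.** This would need a real treatment effect on abuse and unequal exits by arm. Nothing in the protocol establishes either, and MAST concerns alcohol only.
- **No guide for the choice in criterion 3.** The investigator's evaluation in X.B.7 and the risk test in VI.J supply one.
- **The same conflict for alcohol and other illegal drugs.** Those criteria leave the decision to the Site Investigator.
- **Loss of clinical care.** VI.I keeps patients under their VA psychiatrist.

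**Conclusion.** The point holds as an inconsistency of wording with a modest effect. Two rules end study participation and a third may, under a heading about treatment and against the follow-up that VI.E gives to drop-outs and to all patients. The size depends on a frequency the protocol does not state and which is probably small. At an assumed 1% to 5% leaving in the acute phase, at most about 22 to 108 of 2,160 follow-up visits are lost, with full attendance otherwise assumed. The primary endpoint is essentially untouched, apart from the literal recoding of a remitter who is intoxicated at a taper session. Severity is minor to modest.

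**What to change.** Amend X.B.7 as follows.

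1. Visible intoxication and ongoing THC abuse stop study treatment. Misuse of psychiatric medication may do so at the Site Investigator's decision; otherwise the participant is recorded as noncompliant.
2. Failure coding applies only if treatment stops before the end of the acute phase.
3. In all three cases the participant is still followed for protocol assessments, and enters or stays in the 24-week follow-up unless consent is withdrawn.

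Leave the general power to suspend or terminate in VI.I, VI.J and Table 2 footnote 3 as it is, apart from a cross-reference saying that these three events are treatment stops.

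The cost is a few sentences and the remaining scheduled visits for the few patients affected. Some of them will decline, and their data will stay missing.
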